## **Approach for OLE Analysis**

### **Treatment groups:**

There are five treatment groups in the OLE:

Group 1 = old batch for all of OLE (or through ET), N=20

Group 2 = started OLE on old batch, switched at W16 OLE, N=35

Group 3 = started OLE on old batch, switched at W8 OLE, N=26

Group 4 = started OLE on old batch, switched at W4 OLE, N=22

Group 5 = new batch for all of OLE (or through ET), N=46

Total=149, though not all the participants above will be in the mITT analysis, with some being excluded because they do not have at least one efficacy evaluation during the OLE.

In addition, three populations will be evaluated:

1. All participants in OLE
2. OLE participants with screening plasma ptau181 <25.2 pg/mL (2.2 pg/mL in prior version of assay)
3. OLE participants with screening plasma ptau181 < 21 pg/mL (1.8 pg/mL in prior version of assay)

For OLE week 8 data point, groups 1, 2 and 3 will be pooled under “old capsule treatment” and only group 5 will be included under “new capsule treatment” (i.e. only participants with  $\geq 8$  weeks of new capsules will be included).

For the week 16 OLE analysis, groups 1 and 2 will be pooled under the label of “Old Capsules Treatment”, and groups 3, 4 and 5 will be pooled under the label of “New Capsule Treatment” (i.e. all participants with  $\geq 8$  weeks of new capsules will be included for the new capsule treatment group).

The baseline value for all change analyses will be the value at the end of the double-blind period, i.e. at week 16 of the main study (if no value, week 12 will be carried forward).

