### **Analyses to be Conducted**

The primary analyses to be conducted are a comparison of new capsule treatment with old capsule treatment:

- For CGIC, this comparison will be a static, unpaired comparison at week 8 using a parametric test (Mann-Whitney U-test).

- For all other endpoints (CDR-SB, TUG, NPI-10, NTB composite, ISLT immediate, ISLT recognition, UPDRS Motor (Part III), the statistical analysis will be change from baseline using linear mixed effects model with baseline as a covariate, i.e. utilizing data from week 8 and 16 of the OLE. The recommendation would be to utilize the LME model from AscenD-LB (phase 2a), but the Worldwide model from RewinD-LB may also be utilized. In addition, descriptive data (i.e. mean, with sem, change from baseline) with p-values (parametric or non-parametric, as appropriate) for the comparison at each of week 8 and 16 will be provided.

A secondary analysis will be comparing the outcomes during the OLE with outcome during the double-blind period in participants who received placebo during the main study and received  $\geq 8$  weeks of new capsules in the OLE (i.e. received new capsules for either the entire 16 weeks or for 12 weeks starting at week 4):

- For CGIC, the comparison will be a paired comparison of the CGIC score at week 16 of the double-blind period with the CGIC score at week 8 of the OLE utilizing Mann-Whitney U-test.
- For all other endpoints, it will be paired comparison (parametric or non-parametric, as appropriate) of the change from baseline to week 8, and from baseline to week 16. If LME model allows for a within-subject comparison, this would be the preferred method.

Finally, comparison of proportions of progressors (early treatment discontinuation or increase from baseline in CDR-SB of  $\geq 1.5$ ) during the OLE with new capsule treatment vs. old capsule treatment will be conducted. Along with proportion of progressors anytime during the OLE, a Kaplan-Meier analysis of the time to progression may be conducted.

All analyses will be conducted with the observed data at each time point. That is, missing data will not be imputed (e.g., week 8 results being carried forward for missing week 16 data).

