#### *Plasma Biomarkers*

Plasma for biomarker (GFAP, NfL) were obtained at week 8 during the OLE, and will be analyzed as change from baseline (result at week 16 of the double-blind period) for participants treated with new capsules (Group 4 and Group 5 combined) vs. old capsules (Groups 1, 2 and 3; the latter because they received old capsules through to week 8).

In addition, for participants treated with placebo, a within-subject comparison will be made for change from baseline (average of screening and baseline value) to week 12 during placebo treatment compared to change from baseline for OLE (average of week 12 and week 16 of double-blind phase) to week 8 during treatment with either old or new capsules during OLE (the participants who received old vs. new capsules being analyzed separately).

The plasma biomarker data should also be the best opportunity to establish a PK-PD relationship within the participants who received the new capsules at any time within the first eight weeks (for either 4 or 8 weeks).

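### The secondary OLE analysis requires at least 8 weeks of new capsules, yet reads Group 4 at OLE Week 8, when it has had only 4

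*SAP*

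**What the plan says.** The SAP's Approach for OLE Analysis sorts participants into five groups by when, if ever, they moved from old to new capsules. The one that matters here is "Group 4 = started OLE on old batch, switched at W4 OLE, N=22". Group 5 (N=46) took new capsules throughout.

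Under Treatment groups, the grouping is set visit by visit. For the OLE Week 8 data point, Groups 1, 2 and 3 are pooled as old, "and only group 5 will be included under" the new-capsule label. The stated reason is that at least 8 weeks of new capsules are needed. Group 4 is in neither pool at Week 8. It joins the new-capsule pool at Week 16, with Groups 3 and 5.

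Under Analyses to be Conducted, a secondary analysis is described as "comparing the outcomes during the OLE with outcome during the double-blind period in participants who received placebo during the main study". It has the same 8-week minimum and defines the eligible participants as those who "received new capsules for either the entire 16 weeks or for 12 weeks starting at week 4", that is, Groups 5 and 4. For CGIC it is "a paired comparison of the CGIC score at week 16 of the double-blind period with the CGIC score at week 8 of the OLE". For the other endpoints it is a paired comparison "of the change from baseline to week 8, and from baseline to week 16". The OLE baseline for change is the value at the end of the double-blind period.

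**The concern.** The 8-week minimum is tested against a participant's whole time in the OLE, but the outcome is read partway through. Group 4 qualifies on 12 weeks of new capsules, a total it reaches only at Week 16. At Week 8 it has had half of the minimum, and its change from baseline also covers the preceding 4 weeks on old capsules. CGIC has no Week 16 reading in this analysis, so no Group 4 value can meet the condition at the only time it is used.

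What is at stake is interpretation. The OLE plan's main question is whether new and old capsules differ, so it treats them as distinct exposures. A Week 8 result presented as the effect of at least 8 weeks of new capsules would in part reflect participants with a 4-plus-4 mixture. It would also rest on different groups from the Week 8 new-capsule result in the primary OLE comparison.

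**Working it through.** **Inputs** (SAP, Approach for OLE Analysis, Treatment groups): group sizes 20, 35, 26, 22 and 46. The switch is at Week 16 for Group 2, Week 8 for Group 3 and Week 4 for Group 4. Group 1 never switches, and Group 5 is on new capsules from the start.

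**The plan's own total.** 20 + 35 + 26 + 22 + 46 = 149, as stated.

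**Weeks on new capsules at visit t** = max(0, t − switch week):

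| Group | N | New weeks at Week 8 | New weeks at Week 16 |
|---|---|---|---|
| 3 | 26 | 0 | 8 |
| 4 | 22 | 4 (plus 4 old) | 12 (plus 4 old) |
| 5 | 46 | 8 | 16 |

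At Week 8 only Group 5 has 8 weeks of new capsules, which matches the plan's Week 8 grouping. Group 4 meets the condition at Week 16 but not at Week 8. The Plasma Biomarkers text agrees: it gives new-capsule exposure within the first eight weeks as either 4 or 8 weeks.

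**Old-capsule share of exposure in Groups 4 and 5 together**, using all OLE participants:

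- Group 4 share: 22/68 = 32.4%.
- Mean new-capsule time at Week 8: (22×4 + 46×8)/68 = 6.7 of 8 weeks.
- Old-capsule share at Week 8: 22×4/(68×8) = 16.2%.
- Old-capsule share at Week 16: 22×4/(68×16) = 8.1%.

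**Range for the analysed population.** The analysis uses former-placebo participants only, and their split by group is not given. If Group 4 is a fraction s of them, the old-capsule share at Week 8 is s×4/8. Assuming s between 10% and 50%, this runs from 5% to 25%.

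**Effect on the estimate.** Suppose the effect is proportional to weeks on new capsules and old capsules add nothing. Both are assumptions. The Week 8 effect is then (1 − s/2) of the pure new-capsule effect: 95% at s = 10%, 84% at s = 32.4% and 75% at s = 50%.

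**Precision of the paired analysis.** Assume the same variance of the within-person difference in both groups, and former-placebo numbers in the ratio 22:46. Signal relative to noise is then proportional to mean effect × √n. Under proportionality, Groups 4 and 5 give 0.838×√68 = 6.91 and Group 5 alone gives √46 = 6.78. Group 5 alone is therefore about 2% lower. If the effect were complete by 4 weeks, the comparison would be √68 = 8.25 against 6.78, about 18% lower.

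**The case against.** The strongest defence is that the secondary analysis sets its own population. It does not use the old and new labels defined for the primary comparison, and it names the qualifying schedules, so a programmer would know whom to include. Group 4, with 12 weeks, does meet a minimum counted over the OLE. That defence shows the selection is deliberate and reproducible. It does not make a Week 8 reading after 4 new weeks a reading after 8.

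It is also fair that this is an uncontrolled within-person analysis in an open-label extension with no alpha attached, and that every endpoint except CGIC is also read at Week 16, when Group 4 satisfies the condition.

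A reader might go further in three ways that the document does not support.

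- *That Group 3 should be added at Week 16, as in the primary comparison.* Group 3's Week 16 change spans 8 old and 8 new weeks. Adding it would raise the old-capsule share from 8.1% to (22×4 + 26×8)/(94×16) = 19.7%. Leaving it out of a within-person comparison is a reasonable choice.
- *That the biomarker comparison has the same fault.* That section states no 8-week condition and declares its pooling, "for participants treated with new capsules (Group 4 and Group 5 combined) vs. old capsules". It acknowledges the two exposure lengths and intends to use them for a PK-PD relationship.
- *That including Group 4 costs power.* In the paired analysis it does not, even under proportionality (6.91 against 6.78).

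**Conclusion.** The point holds for the secondary Week 8 readings: in full for CGIC, which is read only then, and for the Week 8 changes in the other endpoints. As written, these readings include participants who have not had the 8 weeks of new capsules that the analysis requires and that the Treatment groups section enforces at the same visit.

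Old-capsule time is 5% to 25% of Week 8 exposure over the assumed range for Group 4's share, and 16% at the all-participant share. The matching 95% to 75% for the effect holds only if the effect is proportional to new-capsule weeks and old capsules contribute nothing. The document states neither, so even the direction of any bias is unknown. The 22 and 46 also overstate the numbers analysed, because they include former neflamapimod participants and the document says not all 149 enter the mITT analysis.

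Severity is minor. The Week 16 readings, the primary OLE comparison and the double-blind results are not affected.

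**What to change.** State that, in the secondary analysis, the 8-week minimum is applied at the visit being read. For the CGIC comparison and the Week 8 changes, use Group 5 as the new-capsule group and report Group 4 in a separate row labelled 4 weeks old plus 4 weeks new. Keep Groups 4 and 5 for the Week 16 change, as written. If the preferred mixed model is used instead of separate paired tests, say how Group 4's Week 8 records enter it.

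The cost is a sentence of wording and one table row, and no data are discarded. The main Week 8 row becomes smaller: at most 46 rather than 68 before the restriction to former-placebo participants, or about 23 rather than 34 if half of each group came from placebo (an assumption). No power gain is claimed. The change buys a Week 8 result that is free of old-capsule time and uses the same exposure rule as the primary OLE comparison.

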### 2.2.2 Secondary Endpoints

- Change from Baseline in TUG during the double-blind treatment phase
- Change from Baseline in the composite score of the NTB, including tests of attention and visual learning, during the double-blind treatment phase
- ADCS-CGIC score at Week 16 at the end of the double-blind treatment phase

QMD Ref: Worldwide-TMP-ST-054-1.0_Effective: 12Aug2022	Governing QMD: Worldwide-SOP-ST-026
Confidentiality Statement This document is the property of Worldwide Clinical Trials Inc. and may not be duplicated, copied, altered or removed from company without prior approval from Worldwide Quality Assurance or in compliance with Worldwide Standard Operating Procedures.	

Worldwide Clinical Trials Controlled Quality Management Document		
 WORLDWIDE CLINICAL TRIALS	Sponsor:	EIP Pharma, Inc.
	Protocol Number:	EIP21-NFD-504
STATISTICAL ANALYSIS PLAN		

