C-SSRS, CDR-SB, NTB, TUG, ADCS-CGIC, DCFS, NPI-12, MDS-UPDRS	Day 2 to Day 61	Week 8
	Day 62 to Day 117	Week 16
	Day 118 to Day 229	Week 32

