### 5.10.3.3 *ADCS-CGIC at Week 16 in neflamapimod-treated subjects compared to placebo-recipients*

ADCS-CGIC at Week 16 in neflamapimod vs. placebo will be compared utilizing a two-sided Mann Whitney U test (Wilcoxon Rank Sum Test).

The number of observations in each group, sum of ranks, mean, standard deviation, z-score and corresponding 2-sided p-value will be presented.

```
proc npar1way data= wilcoxon;
  class <treatment>;
  var < ADCS-CGIC at Week 16>;
  ods output WilcoxonScores=scores WilcoxonTest=Wilcoxon;
run;
```

The analysis will be repeated for each subgroup of cholinesterase inhibitor therapy (Yes/No) separately.

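### The paired CGIC comparison in the OLE secondary analysis is assigned the two-sample Mann-Whitney test, which ignores the pairing and most likely costs power

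*SAP*

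**What the plan says.** The secondary analysis under *Analyses to be Conducted* (Approach for OLE Analysis) takes participants who had placebo in the main study and at least 8 weeks of new capsules in the OLE. For CGIC it "will be a paired comparison of the CGIC score at week 16 of the double-blind period". The other half of the pair, and the test to be applied, are given as "CGIC score at week 8 of the OLE utilizing Mann-Whitney U-test".

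Four other places bear on the reading:

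- Section 5.10.3.3, on the double-blind CGIC, says the arms "will be compared utilizing a two-sided Mann Whitney U test (Wilcoxon Rank Sum Test"). The SAP therefore uses the name for the two-independent-samples test.
- The primary OLE comparison of new with old capsules uses the same test for CGIC, and there "this comparison will be a static, unpaired comparison at week 8".
- For all other endpoints of the secondary analysis the plan says "it will be paired comparison (parametric or non-parametric, as appropriate"), and it prefers a within-subject mixed model if one can be fitted.
- On timing, the double-blind endpoint is the "ADCS-CGIC score at Week 16 at the end of the double-blind treatment phase" (Section 2.2.2). For the OLE, "The baseline value for all change analyses will be the value at the end of the double-blind period".

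**The concern.** The same people supply both ratings, and the plan asks for a paired comparison. A rank sum test treats the two sets of ratings as coming from different people. Its variance is therefore wrong whenever the two ratings of one person are correlated, and its p-value does not have the stated meaning. A programmer has to break either the word *paired* or the named test. CGIC is the only endpoint in this analysis tied to a test that discards the pairing.

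A second, separate matter affects how any result would be read. CGIC is itself a rating of change, and the two ratings span different lengths of time.

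**Working it through.** **Inputs.** From the SAP: Group 4 has N=22 and Group 5 has N=46, so 22 + 46 = 68 participants with new capsules from OLE Week 4 or from the start. The five group sizes add up correctly: 20 + 35 + 26 + 22 + 46 = 149. The general significance level is two-sided 5% (Section 5.10.1). CGIC is a 7-point scale on which lower is better (Section 5.2.17). Not in the SAP, and therefore assumed: the number of former-placebo participants among the 68 (taken as half, 34; range 20 to 68), the correlation between the two ratings, the category distribution and the size of the shift. The SAP states no power for this contrast, so there is no figure to reproduce.

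**Step 1: large-sample size of the named test.** The rank sum test uses a variance that assumes independence. The true variance of the paired contrast is about (1 − ρ) times that. The actual two-sided size is therefore 2 × [1 − Φ(1.96 / √(1 − ρ))]. At ρ = 0.5 this is 1.96 / 0.707 = 2.77, giving 0.6%. At ρ = 0 it is 5.0%. At ρ = −0.3 it is 1.96 / 1.140 = 1.72, giving 8.6%.

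**Step 2: simulation on a 7-category scale, 34 pairs.** Correlated normal variables were cut into seven categories, and the power columns use a 0.5 SD shift.

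| Correlation | Mann-Whitney size, large-sample | Mann-Whitney size, simulated | Mann-Whitney power | Signed-rank power |
|---|---|---|---|---|
| −0.3 | 8.6% | 7.9% | 49% | 40% |
| 0 | 5.0% | 4.9% | 48% | 49% |
| 0.3 | 1.9% | 2.3% | 48% | 61% |
| 0.5 | 0.6% | 0.9% | 48% | 73% |
| 0.7 | 0.03% | 0.2% | 48% | 89% |

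Signed-rank size stayed between 3.9% and 5.8% throughout. Repeat runs moved the other figures by a point or two.

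**Step 3: other numbers of pairs.** At correlation 0.5, Mann-Whitney against signed-rank power was 26% against 50% with 20 pairs, 67% against 88% with 48, and 86% against 97% with 68. Mann-Whitney size at that correlation was about 1% in each case.

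**Step 4: rating periods.** The double-blind rating covers 16 weeks. The OLE Week 8 rating covers 8 weeks if made from the end of the double-blind phase, or 16 + 8 = 24 weeks if made from study entry. Neither equals 16. Suppose linear worsening of 0.4 points per 16 weeks and no drug effect:

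- 8-week rating: expected change 0.4 × 8/16 = 0.2, so the contrast is 0.4 − 0.2 = 0.2 points in favour of the OLE.
- 24-week rating: expected change 0.4 × 24/16 = 0.6, so the contrast is 0.2 points against the OLE.

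Doubling the drift to 0.8 doubles both contrasts to 0.4. At drift 0.4, correlation +0.5 and 34 pairs, simulated false rejection was 4.9% with Mann-Whitney and 17.5% with signed-rank.

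**Step 5: is there a matched visit?** Table 2 in Section 5.2.4 maps "C-SSRS, CDR-SB, NTB, TUG, ADCS-CGIC, DCFS, NPI-12, MDS-UPDRS" to OLE Weeks 8, 16 and 32. If rated from the end of the double-blind phase, OLE Week 16 covers 16 weeks. The expected contrast under linear decline is then 0, and signed-rank false rejection was 4.5% to 5.0%. If rated from study entry, it covers 32 weeks and does not match.

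**The case against.** **This may be only a naming slip.** The paired intent is explicit, the next bullet asks for paired methods, and the primary CGIC bullet calls Mann-Whitney a parametric test, so labels in this text are loose. That is fair and makes the repair small. It does not remove the fault, because Section 5.10.3.3 says which test the name denotes and a programmer following the bullet would run it.

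**A reader might infer that the false-positive rate is inflated.** The SAP does not support this as the expected direction. Simulated size reaches about 10% only at correlation −0.5. That value comes from treating CGIC as a difference of two visits, with a random slope (SD g per 16 weeks) plus independent error (SD s). For an 8-week rating from the end of the double-blind phase, the correlation is (0.5g² − s²) / √[(g² + 2s²)(0.25g² + 2s²)]. It equals −0.5 only when g = 0. At g = 2s it is 1/√18 = +0.24. CGIC is a direct rating, so the model shows only that the sign can vary. Negative correlation stays possible but is not the central case.

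**A reader might also fault the SAP for not giving the OLE CGIC reference point.** That may be set in the protocol, which is not at hand, and is not raised here. The unequal periods hold under either reference point, but their direction and size depend on it and on an assumed drift.

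**Changing the test alone does not make the contrast sound.** This stands. With unequal periods and positive correlation, the signed-rank test is more likely to declare a difference that comes from time alone.

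**Conclusion.** The contradiction between a paired design and a two-sample test is in the text and rests on no assumption. Its likely effect is conservatism and lost power: with 34 pairs, about 13, 25 and 41 percentage points of power (61, 73 and 89 minus 48) at correlations 0.3, 0.5 and 0.7. Those sizes depend on the assumed number of pairs, correlation, category distribution and 0.5 SD shift. If the correlation were negative, the test would be anti-conservative instead.

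The unequal rating periods are a conditional caution, not a second proven error. A difference in period can by itself produce a significant result, whose direction depends on the reference point.

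The scope is one endpoint of a secondary, open-label analysis. Nothing here touches the double-blind results, or the primary new-versus-old OLE comparison, where a two-sample test suits the design. The correction should be made, but it is not critical to the trial's conclusions.

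**What to change.** In the CGIC bullet of the secondary OLE analysis, replace the Mann-Whitney test with the two-sided Wilcoxon signed-rank test on within-participant differences, in participants with both ratings observed.

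Add one conditional sentence on the periods. If the OLE CGIC is rated from the end of the double-blind phase, as the OLE baseline rule suggests, also compare double-blind Week 16 with the scheduled OLE Week 16 rating, which matches the 16-week period. If it is rated from study entry, keep the Week 8 contrast and state that the two ratings cover 16 and 24 weeks.

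The cost is one changed phrase, a sentence or two and a rerun on ratings already scheduled. Section 5 of the SAP already provides for recording changes after database lock in an addendum. There may be fewer pairs at OLE Week 16 than at Week 8; the SAP gives no figure.

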#### *Plasma Biomarkers*

Plasma for biomarker (GFAP, NfL) were obtained at week 8 during the OLE, and will be analyzed as change from baseline (result at week 16 of the double-blind period) for participants treated with new capsules (Group 4 and Group 5 combined) vs. old capsules (Groups 1, 2 and 3; the latter because they received old capsules through to week 8).

In addition, for participants treated with placebo, a within-subject comparison will be made for change from baseline (average of screening and baseline value) to week 12 during placebo treatment compared to change from baseline for OLE (average of week 12 and week 16 of double-blind phase) to week 8 during treatment with either old or new capsules during OLE (the participants who received old vs. new capsules being analyzed separately).

The plasma biomarker data should also be the best opportunity to establish a PK-PD relationship within the participants who received the new capsules at any time within the first eight weeks (for either 4 or 8 weeks).

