### **5.11 Pharmacokinetic and Biomarker Analyses**

A listing of plasma trough concentrations will be presented for the PK Analysis Set. Plasma biomarker analysis will be defined separately and will not be part of this SAP.

QMD Ref: Worldwide-TMP-ST-054-1.0 Effective: 12Aug2022	Governing QMD: Worldwide-SOP-ST-026
Confidentiality Statement	
This document is the property of Worldwide Clinical Trials Inc. and may not be duplicated, copied, altered or removed from company without prior approval from Worldwide Quality Assurance or in compliance with Worldwide Standard Operating Procedures.	

Worldwide Clinical Trials Controlled Quality Management Document		
 WORLDWIDE CLINICAL TRIALS	Sponsor:	EIP Pharma, Inc.
	Protocol Number:	EIP21-NFD-504
STATISTICAL ANALYSIS PLAN		

Note: Glial Fibrillary Acidic Protein (GFAP) and Neurofilament light (NfL) levels will be measured in pre-treatment, week 12 and week 16 and the results analyzed for treatment effects concurrently with the primary efficacy analysis.

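### The new- versus old-capsule comparison of GFAP and NfL uses change from the Week 16 value alone and states no baseline covariate; ANCOVA on the Week 16 and Week 12 values is more precise, by an uncertain amount

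*SAP*

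**What the plan says.** The comparison is in the SAP's Approach for OLE Analysis, under Plasma Biomarkers. Samples taken at OLE Week 8 are compared between new capsules (Groups 4 and 5) and old capsules (Groups 1, 2 and 3), and they "will be analyzed as change from baseline (result at week 16 of the double-blind period"). No model, test or covariate is named.

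Four other places bear on this:

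- **General OLE baseline rule (Treatment groups).** Baseline for every change analysis is the end of the double-blind period, "i.e. at week 16 of the main study (if no value, week 12 will be carried forward").
- **Next paragraph of Plasma Biomarkers.** A separate within-subject analysis of placebo participants uses "change from baseline for OLE (average of week 12 and week 16 of double-blind phase) to week 8".
- **Analyses to be Conducted.** For a listed set of clinical endpoints, "the statistical analysis will be change from baseline using linear mixed effects model with baseline as a covariate". GFAP and NfL are not in that list.
- **Section 5.11.** GFAP and NfL "levels will be measured in pre-treatment, week 12 and week 16". The same section says: "Plasma biomarker analysis will be defined separately and will not be part of this SAP".

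**The concern.** A change score from one earlier sample fixes the coefficient on that sample at 1 and gives every other earlier sample a weight of 0. Any assay noise or short-term fluctuation in the Week 16 value passes in full into the outcome. A second double-blind sample is planned, and the plan already treats baseline as a covariate when it compares capsules on the clinical endpoints, so the biomarker comparison appears to give up precision for no stated reason.

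At most 68 participants on new capsules and 81 on old capsules contribute. They are grouped by capsule batch and switch time, so their starting levels may differ. Whether and how the analysis adjusts for starting level then affects both the width of the interval and the estimate itself, and the text should settle it.

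**Working it through.** **Inputs from the documents.** Group sizes (Treatment groups): 20, 35, 26, 22 and 46. They sum to 149, which agrees with the stated total. Old capsules: 20 + 35 + 26 = 81. New capsules: 22 + 46 = 68. Sampling times: double-blind Week 12, double-blind Week 16 and OLE Week 8, so Week 16 precedes the outcome by 8 weeks and Week 12 precedes it by 12.

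**Inputs not in the documents.** The SAP gives no standard deviation or correlation for GFAP or NfL. Below, each visit has variance 1 and the correlation is varied. The quantity of interest is the per-participant variance. The variance of the group difference is that value times (1/81 + 1/68), so ratios carry over unchanged.

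**Case A: the same correlation ρ between every pair of visits.**

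- Change from Week 16: 2(1 − ρ).
- ANCOVA on Week 16 and Week 12: 1 − 2ρ²/(1 + ρ).

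**Case B: serial decay, correlation r per four weeks.** The outcome correlates r² with Week 16 and r³ with Week 12.

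- Change from Week 16: 2(1 − r²).
- ANCOVA on both: 1 − r⁴. Week 12 adds nothing once Week 16 is in the model.
- Ratio: (1 + r²)/2, so the saving is (1 − r²)/2.

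| Case | Correlation | Change from Week 16 | ANCOVA on both | Ratio | Saving |
|---|---|---|---|---|---|
| A | 0.70 | 0.600 | 0.424 | 0.706 | 29% |
| A | 0.80 | 0.400 | 0.289 | 0.722 | 28% |
| A | 0.90 | 0.200 | 0.147 | 0.737 | 26% |
| A | 0.95 | 0.100 | 0.074 | 0.744 | 26% |
| B | 0.70 | 1.020 | 0.760 | 0.745 | 25.5% |
| B | 0.80 | 0.720 | 0.590 | 0.820 | 18% |
| B | 0.90 | 0.380 | 0.344 | 0.905 | 9.5% |
| B | 0.95 | 0.195 | 0.185 | 0.951 | 4.9% |
| B | 0.98 | 0.079 | 0.078 | 0.980 | 2.0% |

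**In between.** Six mixtures were tried, each with a stable between-person part (0.5 to 0.8 of the variance), a serially decaying part (0.05 to 0.4, r of 0.8 or 0.9) and measurement error (0.1 to 0.2). The ratio for ANCOVA on both values was 0.746 to 0.837, a saving of 16% to 25%.

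**Separate covariates or their mean?** In Case A the two are identical. In Case B, ANCOVA on the mean has variance 1 − r⁴(1 + r)/2. At r = 0.95 that is 1 − 0.8145 × 0.975 = 0.206, against 0.195 for the raw change: a ratio of 1.06, which is a loss. Raw change from the averaged baseline has ratio 0.75 throughout Case A, but 1.00 to 1.12 in Case B. Separate covariates avoid this, because raw change from Week 16 is the special case with coefficients 1 and 0. Fitting the coefficients therefore cannot raise the residual variance, apart from the degrees of freedom spent.

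**Week 16 alone as covariate.** In Case A the ratio is (1 + ρ)/2, a saving of 15%, 10% and 5% at 0.7, 0.8 and 0.9. Most of the Case A gain at those correlations therefore comes from using the second sample.

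**What a favourable case would buy.** At a ratio of 0.75, an effect with 80% power under the raw change has standardised distance (1.960 + 0.842)/√0.75 = 3.235. Power is then Φ(3.235 − 1.960), about 90%.

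**The case against.** - **The plan does not exclude adjustment.** A reader might infer that the biomarkers are to be analysed without baseline adjustment. The text is silent: it names no model, and the plan uses the same change-from-baseline language for clinical endpoints that do carry "linear mixed effects model with baseline as a covariate". Section 5.11 also defers biomarker analysis to a separate definition. This stands as to wording: the covariate is unstated, not ruled out. It does not remove the point, because Plasma Biomarkers is where these documents set out the OLE comparison and the model is open there.
- **Week 16 follows the plan's own rule.** A reader might take the two OLE baselines as a contradiction. The between-group comparison follows the general Week 16 rule. The averaged baseline belongs to a different analysis, which sets a two-sample baseline before placebo against a two-sample baseline before the OLE. This stands. The averaged version still departs from a rule written for all change analyses, so a sentence of explanation would help.
- **The gain may be small.** This stands. The 26% to 29% needs equal variances and one common correlation, and the visits are unequally spaced. With strong serial decay little is saved.
- **ANCOVA is not free here.** No randomisation to capsule groups is described, so differences in starting level cannot be treated as chance. If they are systematic, ANCOVA and the change score may answer different questions. This stands, and is why both should be shown.
- **Limited role.** The comparison is open-label, with no stated threshold or power. That lowers the priority but does not favour the less efficient method.

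**Conclusion.** The point holds as one of precision and of an unstated model. The biomarker capsule comparison is set as change from one value, while a second double-blind sample is planned and the clinical endpoints in the corresponding comparison have a baseline covariate.

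The size rests wholly on assumed correlations. The saving in variance is about 26% to 29% with equal correlation of 0.7 to 0.95, and about 26% down to 2% with serial decay of 0.7 to 0.98 per four weeks. A reader might conclude that a quarter of the variance is simply avoidable, or that averaging Weeks 12 and 16 is the cure. The documents support neither: they give no correlations, and under serial decay averaging can lose precision. Nor do they support calling any imbalance in starting level a chance imbalance. Nothing here shows the planned comparison to be biased or invalid because of the Week 16 baseline.

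**What to change.** State the model under Plasma Biomarkers. Compare OLE Week 8 GFAP and NfL between Groups 4 and 5 and Groups 1, 2 and 3 by ANCOVA, with the double-blind Week 16 and Week 12 values as two separate covariates, not their mean. If one value is missing, use the other. With Week 16 in the model, taking Week 8 or its change from Week 16 as the outcome gives the same group difference.

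Report the unadjusted change from Week 16 as a supporting analysis. If the two disagree, show starting levels by capsule group and say that the estimates may differ because the groups did not start alike. Add a sentence on why the placebo within-subject analysis uses an averaged baseline.

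The cost is a sentence or two of text, one or two degrees of freedom and one supporting estimate per marker. No new samples are needed.
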